1.2.9.1 Experience with avelumab in refractory metastatic urothelial carcinoma

Sixty-six patients with metastatic urothelial carcinoma were studied with avelumab(30). An independent central review assessment resulted in a confirmed ORR of 18.2% including 5 patients (11.4%) with a complete response (**Figure 3**). Three patients (6.8%) had a partial response and 15 patients had stable disease as best response. Patients' responses were predominantly found in those with PD-L1 positive tumors. Seven of eight responding patients (87.5%) had PD-L1 positive tumors whereas only 4.7% (1 of 24) of patients with PD-L1 negative tumors had a response. The median time to response was 13.0 weeks. The median duration of response was not reached.

1.2.9.2 Experience with avelumab in ovarian cancer

A total of 124 relapsed ovarian cancer patients were treated with avelumab resulting in a response rate of 9.7% comprised of 12 partial responses with 6 ongoing. Stable disease was observed in 44% yielding a disease control rate of 54% (unpublished data).

1.2.9.3 Experience with avelumab in non-small cell lung cancer (NSCLC)

In a Phase 1b trial of 184 patients, objective responses were observed in 22 (12%) patients, 1 CR, 21 PRs, and stable disease was found in 70 patients (38%)(39). Overall, 50% of patients achieved disease control. The most common treatment-related AEs of any grade were fatigue (25%), infusion reactions (21%), and nausea (13%). Grade 3 or worse treatment-related AEs occurred in 13% of patients, with the most common being infusion reactions (2%) and increased lipase level (2%).

1.2.9.4 Experience with avelumab in breast cancer

Avelumab was studied in 168 patients with locally advanced breast cancer or MVC refractory to or progressing after standard of care. Response rate in the entire cohort was 5.4% (9 patients) with

1 complete and 8 partial responses. Stable disease was observed in an additional 40 patients (23.8%) yielding an overall disease control rate of 29.2%. Responses were predominantly in PD-L1 expressing tumors (unpublished data).

1.2.9.5 Experience of with avelumab in Merkel cell carcinoma

Merkel cell carcinoma (MCC) is a rare aggressive neuroendocrine tumor of the skin. The proportion of patients who achieved an objective response was 28/88 (31.8%) including 8 complete and 20 partial responses(34).

Further trials of avelumab for mesothelioma, gastric cancer, adrenocortical carcinoma and renal cancer are ongoing.

[figure not shown]

Figure 3: Clinical activity of avelumab. (A) Time to response, duration of treatment, and duration of response to avelumab (eight confirmed responses and four unconfirmed responses as of data cutoff), with PD-L1 expression status indicated (on the basis of a >5% staining threshold on tumor cells; non-evaluable specimens [n = 7] included those that were missing, of poor quality, or otherwise not available to provide results). The vertical dotted line represents 1 year from the initiation of treatment. (B) Plot of tumor regression from baseline as measured by Response Evaluation Criteria in Solid Tumors (RECIST) in all assessable patients (n = 38), with PD-L1 expression status indicated (on the basis of a >5% staining

threshold on tumor cells). ECOG performance status, presence of non-lymph node metastasis, and albumin and hemoglobin levels at baseline are shown for each patient. The upper dotted line represents progression at 20% and the lower dotted line represents the RECIST boundary for complete response or partial response at 30%. (C) Percentage change in sum of target lesion diameters from baseline over time for all assessable patients (n = 38), defined as those patients with baseline tumor assessments and at least one post- baseline assessment. The upper dotted line represents progression at 20% and the lower dotted line represents the RECIST boundary for complete response or partial response at 30%. (30)

1.2.9.6 Immune related risks

In addition, some clinically relevant irAEs were reported after the data cutoff or outside of the Pooled Safety Dataset. These included: 3 events of nonfatal graft versus host disease (2 in the liver and 1 in skin) and 1 event of immune thrombocytopenic purpura in Study B9991007 (avelumab in subjects with cHL), 4 events of myasthenia gravis/myasthenic syndrome in the clinical studies, and overall 15 events of pancreatitis including one case of fatal pancreatitis necrotising in Study B9991003 with the combination of avelumab with axitinib in subjects with RCC (Investigator Brochure, 29May 2020).

1.2.10 Rationale of Study

1.2.10.1 PD-L1 expression in T-cell malignancies

Several IHC analyses have demonstrated that T-cell lymphomas express PD-L1. In a series of 26 cases of cutaneous T-cell lymphoma (CTCL), virtually all stages showed staining for PD-L1 in the majority of atypical lymphocytes (>50% in 5/7 stage I/II, 6/6 stage III, and 11/11 stage IV)(40). An older series of 11 patients with CTCL (stage unspecified), and 65 patients with peripheral T-cell lymphoma-NOS reported 17-27% PD-L1 positivity by immunohistochemistry with a cutoff of 30%(41). Low prevalence of PD-L1 expression in PTCL-NOS was confirmed in a series of 11 patients, with three (28%) being positive using a $\geq 5\%$ cutoff(42).

Eighteen of 24 patients with ALK-negative ALCL showed PD-L1 expression as assessed by IHC using SP142 antibody (Ventana). Interestingly, FISH analysis showed no PD-L1 gene amplification, but *in silico* analysis of the PD-L1 and PD-L2 gene promoters identified multiple potential binding sites for STAT3 and MYC(43). Multiple other analyses of the T-cell lymphoma genomic landscape did not find mutations or gene copy alterations of the PD-L1-encoding PDCD1 gene(44-48). Some studies found alterations in the PD-1 encoding PDCD1 gene in 8-36% of patients with T-cell lymphoma.

Since a significant number of T-cell malignancies express PD-L1, and since the anti-PD-L1 antibody avelumab has shown ADCC activity *in vitro*, agents that may enhance ADCC by increasing number and activity of Fc-binding effector cells — such as rhIL15 — could improve efficacy of avelumab in these diseases.

1.2.10.2 Preclinical Trials of IL-15 with Anticancer Monoclonal Antibodies to Augment their ADCC

While the *in vivo* effects of IL-15 in cancer patients are still not entirely clear, the initial clinical data has demonstrated that to achieve its full potential in the treatment of cancer, IL-15 will have to be used in combination with other therapeutic agents. In light of the data from preclinical animal models and clinical trials of the capacity of IL-15 to increase the number of activated NK cells, T cells and monocytes, this information supports the administration of IL-15 with antitumor monoclonal antibodies to augment their ADCC against tumor cells. To further investigate this

strategy, the [name] Laboratory used an immunocompetent syngeneic mouse model of B-cell lymphoma to investigate the combination of IL-15 with rituximab. Wild-type CD56 and BL/6 mice were inoculated intravenously with EL4-CD20 cells, a mouse lymphoma line transfected with CD20. The mice were distributed into 4 treatment groups (control, IL-15 alone, rituximab alone and the combination) of 10 mice each. IL-15(5 µg/mouse) was administered 5 x per week for 4 weeks beginning 3 days after EL4-CD20 inoculation. In cohorts receiving rituximab, the monoclonal antibody was given once per week for 4 weeks starting 5 days after EL4-CD20 inoculation. As seen (**Figure 4**), IL-15 or rituximab monotherapy prolonged survival of mice when compared to the control group ($p < 0.05$) but the combination of IL-15 and rituximab showed the greatest prolongation of survival compared to monotherapies (< 0.01), such that 75 days after tumor inoculation 90% of the combination treatment group were still alive in contrast to 30% survival from the monotherapy groups and no surviving mice in the control group (**Figure 4**). In a parallel preclinical trial, the [name] Group administered a combination therapy of alemtuzumab with rhIL-15 in the MET-1 bearing xenograft model in wild-type SCID/NOD mice (**Figure 5**). Again, there was an augmentation of survival of the combination of IL-15 with alemtuzumab compared to either element alone. The efficacy was lost in FcRγ^{-/-} mice, further supporting the hypothesis that the efficacy was due to augmented ADCC.

Additionally, Jochems C, et al. analyzed the in vitro ADCC capacity of an IgG1 anti-PD-L1 antibody structurally similar to avelumab with and without IL-15, and compared it to that of a fusion protein consisting of the anti-PD-L1 and a TGF-beta trap(49). IL-15/IL-15R alpha IgFc enhanced the ADCC capacity of both molecules, making them equal.

[figure not shown]

Figure 4: Addition of IL-15 increased ADCC and antitumor efficacy of cancer-directed monoclonal antibodies. EL4 leukemic cells were transfected with human CD20 and administered intravenously into immunologically intact mice. Mice treated with either IL-15 alone (yellow) or rituximab (anti-CD20) alone (red) showed modest prolongation of survival. This prolongation was markedly augmented when the two agents were administered together (green).

[figure not shown]

Figure 5: Combination alemtuzumab and rhIL-15 in a xenograft model of MET-1 ATL Leukemia.

On the left: SCID/NOD mice bearing the MET-1 ATL leukemia who received either alemtuzumab (CAMPATH) (red) or IL-15 alone (yellow) had only modest efficacy that was markedly augmented by the combination of IL-15 plus alemtuzumab (green). Right: This efficacy was lost in $\text{FcR}\gamma^{-/-}$ mice supporting the hypothesis that the efficacy was due to ADCC.

2 ELIGIBILITY ASSESSMENT AND ENROLLMENT

2.1 ELIGIBILITY CRITERIA

2.1.1 Inclusion Criteria

2.1.1.1 Patients must have histologically or cytologically proven relapsed/refractory T-cell lymphoma other than adult T-cell leukemia/lymphoma (ATLL), angioimmunoblastic T-cell lymphoma (AITL), peripheral T-cell lymphoma T follicular helper phenotype (PTCL-TFH), or enteropathy-associated T-cell lymphoma (EATL), confirmed by the Laboratory of Pathology, NCI

2.1.1.2 Patients with CD30+ mycosis fungoides/Sézary syndrome (MF/SS) or CD30+ anaplastic large cell lymphoma (ALCL) must have relapsed after or become intolerant to treatment with brentuximab vedotin.

2.1.1.3 A formalin fixed tissue block or 15 slides of tumor sample (archival or fresh) must be available for performance of correlative studies. **NOTE:** Patients must be willing to have a tumor biopsy if prior tissue or adequate archival tissue is not available (i.e., post-enrollment and prior to treatment).

2.1.1.4 Disease must be measurable with at least one measurable lesion by RECIL 2017 or mSWAT criteria (see Section [6.3](#)), or have an abnormal clonal T-cell population detectable by peripheral blood flow cytometry

2.1.1.5 Age \geq 18 years

NOTE: Because no dosing or adverse event data are currently available on the use of rhIL-15 in combination with avelumab in patients $<$ 18 years of age, children are excluded from this study, but will be eligible for future pediatric trials

2.1.1.6 ECOG performance status \leq 1 (Karnofsky \geq 80%, see [APPENDIX A](#)).

2.1.1.7 Adequate organ and marrow function as defined below:

Absolute neutrophil count	$>$ 1,000/mcL
Absolute lymphocyte count	\geq 500/mcL
Hemoglobin	\geq 9 g/dL
Platelets	$>$ 100,000/mcL
Total bilirubin	\leq 1.5 X institutional upper limit of normal (ULN)
AST(SGOT)/ALT(SGPT)	\leq 2.5 X institutional ULN
Serum creatinine	\leq 1.5 X institutional ULN
OR	
Creatinine clearance	\geq 50 mL/min/1.73 m ² for patients with creatinine levels $>$ 1.5 institutional ULN

2.1.1.8 Negative serum or urine pregnancy test at screening for women of childbearing potential (WOCBP)

NOTE: WOCBP is defined as any female who has experienced menarche and who has not undergone successful surgical sterilization or who is not postmenopausal. WOCBP must have a negative pregnancy test (HCG blood or urine) during screening.

2.1.1.9 Women of child-bearing potential and men must agree to use adequate contraception (hormonal or barrier method of birth control; abstinence) prior to study entry, for the duration of study participation, and 30 days after completion of rhIL-15 and avelumab administration. Should a woman become pregnant or suspect she is pregnant while she or her partner is participating in this study, she should inform her treating physician immediately.

2.1.1.10 Ability of subject to understand and the willingness to sign a written informed consent document

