2.1.2.4 Patients who are receiving any other investigational agents

2.1.2.5 Patients who have had prior therapy with any antibody/drug targeting PD-1/PD-L1 T-cell coregulatory proteins (immune checkpoints)

2.1.2.6 Current use of immunosuppressive medication, EXCEPT for the following:

- Intranasal, inhaled, topical steroids, or local steroid injection (e.g., intra-articular injection)
- Systemic corticosteroids at physiologic doses ≤ 10 mg/day of prednisone or equivalent; or,
- Steroids as premedication for hypersensitivity reactions (e.g., CT scan premedication)

- 2.1.2.7 Patients with known CNS involvement should be excluded from this clinical trial because of their poor prognosis and because they often develop progressive neurologic dysfunction that would confound the evaluation of neurologic and other adverse events
- 2.1.2.8 Patients with previous malignant disease other than the target malignancy within the last 5 years with the exception of basal or squamous cell carcinoma of the skin or cervical carcinoma in situ
- 2.1.2.9 Patients with history of any organ transplantation, including allogenic stem cell transplantation
- 2.1.2.10 Received a live vaccine within 4 weeks of the first dose of avelumab. Vaccination with a live vaccine while on trial is prohibited. **NOTE:** Seasonal influenza vaccines for injection are generally inactivated flu vaccines and are allowed; however intranasal influenza vaccines (e.g., Flu-Mist®) are live attenuated vaccines, and are not allowed
- 2.1.2.11 Patients with history of allergic reactions attributed to compounds of similar chemical or biologic composition to rhIL-15 or avelumab
- 2.1.2.12 Patients with uncontrolled intercurrent illness including, but not limited to, ongoing or active infection requiring systemic therapy, or psychiatric illness/social situations that would limit compliance with study requirements
- 2.1.2.13 Inability or refusal to practice effective contraception during therapy or the presence of pregnancy or active breastfeeding. Based on its mechanism of action, avelumab can cause fetal harm when administered to a pregnant woman. Animal studies have demonstrated that inhibition of the PD-1/PD-L1 pathway can lead to increased risk of immune-mediated rejection of the developing fetus resulting in fetal death. These potential risks may also apply to other agents used in this study

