3.3 DOSE MODIFICATIONS

If one study agent is held, the other must be held as well. The maximum time agents may be held cannot exceed 6 weeks. Patients who exceed 6 weeks must be removed from the study (section 3.7).

3.3.1 rhIL-15-specific Adverse Events

Please refer to the Comprehensive Adverse Event and Potential Risk list (CAEPR) for rhIL-15 presented in Section 14.1.2.

Dose of rhIL-15 is based on the dose level and patient's weight at the beginning of each cycle and can only be modified for rounding and/or consistency with prior cycles, and not for adverse events or renal/hepatic dysfunction. Infusion may continue during correction of electrolyte and other laboratory abnormalities listed in Section 3.1.1. Infusion may be interrupted for up to two hours each day, but treatment should end 120 (± 1) hours after initiation on Day 1.

Note: IL-15 should not be administered within 1 week of steroid administration when steroids are given to treat avelumab toxicities as listed in the Section 3.3.2.

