Table 9: Treatment Modifications for Hepatic Immune-related AEs

Hepatic irAEs		
Liver test elevation	Initial Management	Follow-up Management
Grade 1 Grade 1 AST or ALT $>$ ULN to 3.0 \times ULN and/or total bilirubin $>$ ULN to 1.5 \times ULN	Continue avelumab	Continue liver function monitoring If worsens: Treat as Grade 2 or 3 to 4
Grade 2 AST or ALT $>$ 3.0 to \leq 5 \times ULN and/or total bilirubin $>$ 1.5 to \leq 3 \times ULN	Withhold avelumab Increase frequency of monitoring to every 3 days	If returns to Grade \leq 1: Resume routine monitoring, resume avelumab If elevations persist $>$ 5 to 7 days or worsen: Treat as Grade 3 or 4
Grade 3 to 4 AST or ALT $>$ 5 \times ULN and/or total bilirubin $>$ 3 \times ULN	Permanently discontinue protocol therapy Increase frequency of monitoring to every 1 to 2 days 1 to 2 mg/kg/day prednisone PO, or PO/IV equivalent Add prophylactic antibiotics for opportunistic infections Consult gastroenterologist/hepatologist Consider obtaining MRI/CT scan of liver and liver biopsy if clinically warranted	If returns to Grade \leq 1: Taper steroids over at least 1 month and add prophylactic antibiotics for opportunistic infections If does not improve in $>$ 3 to 5 days, worsens or rebounds: Add mycophenolate mofetil 1 gram (g) twice daily If no response within an additional 3 to 5 days, consider other immunosuppressants per local guidelines

Table 10: Treatment Modifications for Renal Immune-related AEs

Renal irAEs		
Creatinine Increase	Initial Management	Follow-up Management
Grade 1 Creatinine increased > ULN to 1.5 x ULN	Continue avelumab	Continue renal function monitoring If worsens: Treat as Grade 2 or 3 to 4
Grade 2 to 3 Creatinine increased > 1.5 and ≤ 6 x ULN	Withhold avelumab Increase frequency of monitoring to every 3 days 1 to 2 mg/kg/day prednisone PO, or PO/IV equivalent. Add prophylactic antibiotics for opportunistic infections Consider renal biopsy	If returns to Grade ≤1: Taper steroids over at least 1 month, and resume avelumab following steroids taper. If worsens: Treat as Grade 4.
Grade 4 Creatinine increased > 6 x ULN	Permanently discontinue protocol therapy Monitor creatinine daily 1 to 2 mg/kg/day prednisone PO, or PO/IV equivalent. Add prophylactic antibiotics for opportunistic infections Consider renal biopsy Nephrology consult	If improves to Grade ≤ 1: Taper steroids over at least 1 month

Table 11: Treatment Modifications for Cardiac Immune-related AEs

Cardiac irAEs		

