Grade 2 or Grade 3 clinical signs or symptoms suggestive of a potential irAE	Withhold avelumab pending clinical investigation	If irAE is ruled out, manage as appropriate according to the diagnosis and consider re-starting avelumab If irAE is confirmed, treat as Grade 2 or 3 irAE.
Grade 2 irAE Or first occurrence of Grade 3 irAE	Withhold avelumab 1 to 2 mg/kg/day prednisone PO, or PO/IV equivalent. Add prophylactic antibiotics for opportunistic infections Specialty consult as appropriate	If returns to Grade ≤ 1 : Taper steroids over at least 1 month, and resume avelumab following steroids taper.

Other irAEs (not described above)		
Grade of other irAEs (NCI CTCAE v5)	Initial Management	Follow-up Management
Recurrence of same Grade 3 irAEs	Permanently discontinue protocol therapy 1 to 2 mg/kg/day prednisone PO or PO/IV equivalent. Add prophylactic antibiotics for opportunistic infections Specialty consult as appropriate	If returns to Grade ≤ 1 : Taper steroids over at least 1 month
Grade 4	Permanently discontinue protocol therapy 1 to 2 mg/kg/day prednisone PO, or PO/IV equivalent and/or other immunosuppressant as needed. Add prophylactic antibiotics for opportunistic infections Specialty consult	If improves to Grade ≤ 1 : Taper steroids over at least 1 month
Requirement for 10 mg per day or greater prednisone or equivalent for more than 12 weeks for reasons other than hormonal replacement for adrenal insufficiency Persistent Grade 2 or 3 irAE lasting 12 weeks or longer	Permanently discontinue protocol therapy Specialty consult	

Abbreviations: ACTH=adrenocorticotrophic hormone; ADL=activities of daily living; ALT=alanine aminotransferase; AST=aspartate aminotransferase; BNP=B-type natriuretic peptide; CK-MB=creatinine kinase MB; CT= computed tomography; FSH=follicle-stimulating hormone; GH=growth hormone; IGF-1=insulin-like growth factor 1; irAE=immune related adverse event; IV=intravenous; LH=luteinizing hormone; MRI=magnetic resonance imaging; NCI CTCAE=National Cancer Institute Common Terminology Criteria for Adverse Events; PRL=prolactin; T4=thyroxine; TSH=thyroid stimulating hormone; ULN=upper limit of normal.

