10.2 SAMPLE SIZE DETERMINATION

The MTD will be based on the assessment of DLT during the first cycle of treatment and will be defined as the dose level at which less than one-third of patients (0 of 3 or 0-1/6 patients) treated experience a DLT, with the next higher dose level demonstrating one-third or a greater number of patients ($\geq 2-3$ or $\geq 2-6$ patients) having a DLT. If a subject did not experience a DLT and did not finish one cycle of treatment (28 days) he or she will not be evaluable for determination of the MTD and would be replaced in the dose level. An additional 3 to 6 patients will be enrolled at the MTD, so that a total of 9 patients will be treated at this dose.

Using this dose-escalation scheme the probability of escalating to the next dose level will be based on the true rate of DLT at the current doses given by the following table (each group will be considered independently of the other); Thus, if the true underlying proportion of DLTs is 50% at the current dose there is a 17% probability of escalating to the next dose.

True toxicity at a given dose	10%	20%	30%	40%	50%	60%
Probability of escalating	0.91	0.71	0.49	0.31	0.17	0.08

If all four dose levels are evaluated with 6 patients per dose level and 9 total patients at the MTD, a maximum of 27 evaluable patients will be enrolled. Similarly, if all dose levels are evaluated with 3 patients per dose level and 9 total patients at the MTD, the minimum number of evaluable patients required will be 18. To account of unevaluable patients, accrual ceiling will be set at 30. It is expected that the accrual can be completed in 24 months.

A maximum of 30 patients will be enrolled over 24 months, at a rate of 1-2 patients per month.

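### Patients enrolled through the creatinine-clearance route (serum creatinine above 1.5 x ULN) meet a renal hold rule in Table 10 whose resume point lies below their own entry value

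*Combined protocol and SAP*

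**What the plan says.** **Entry.** Section 2.1.1.7 accepts serum creatinine up to 1.5 x ULN. As an alternative it accepts a clearance of at least 50 mL/min/1.73 m² "for patients with creatinine levels $>$ 1.5 institutional ULN". This alternative has no upper limit on serum creatinine. It is a working route: Sections 2.2.3 and 2.4.2 schedule a 24-hour urine clearance for patients with raised serum creatinine.

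**Hold.** Table 10 in Section 3.3.2.2, on renal immune-related adverse events, defines its Grade 2 to 3 row as "Creatinine increased > 1.5 and ≤ 6 x ULN". The action is "Withhold avelumab Increase frequency of monitoring to every 3 days 1 to 2 mg/kg/day prednisone PO, or PO/IV equivalent".

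**Resume.** If creatinine comes back to Grade 1 or lower, which Table 10 sets at no more than 1.5 x ULN, the instruction is "Taper steroids over at least 1 month, and resume avelumab following steroids taper". No row of Table 10 refers to the patient's baseline.

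**Joint hold and time limit.** Section 3.3 states "If one study agent is held, the other must be held as well" and allows a hold of at most 6 weeks before removal. It also bars rhIL-15 within 1 week of steroids given for avelumab toxicity.

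**MTD set.** Under Section 10.2, of a patient who has no DLT and does not finish the 28-day first cycle, "he or she will not be evaluable for determination of the MTD and would be replaced".

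**The concern.** The second branch of the creatinine criterion begins exactly where the hold row of Table 10 begins. A patient enrolled through that branch has no Grade 1 band to pass through. The first rise that an investigator attributes to an immune cause is already in the row that calls for a hold and systemic steroids. The patient must then reach a creatinine lower than the one at enrolment before treatment can restart.

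Such a rise is foreseeable. Section 14.1.8 lists increased creatinine among the possible effects of rhIL-15, and Section 14.2.2 does the same for avelumab.

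Two things are at stake. An eligible patient could receive systemic steroids and lose both agents under a recovery test that returning fully to baseline would not satisfy. In the escalation phase, a loss of this kind in cycle 1 could take the patient out of the MTD count for a reason that the design did not intend.

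**Working it through.** No figure in the plan lies behind this point, so the check compares threshold ranges.

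**1. Overlap of entry and hold ranges (multiples of ULN).**
- First entry branch, up to 1.5, against the hold row, above 1.5 to 6: no overlap.
- Clearance branch, above 1.5, against the same row: every entry value from just above 1.5 up to 6 lies inside it.
- For comparison, AST/ALT entry is up to 2.5 and the Table 9 hold starts above 3.0; bilirubin entry is up to 1.5 and the hold starts above 1.5. Neither overlaps. Of these limits, creatinine is the exception.

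**2. Fall below entry needed to resume.** With entry value c (x ULN), the required fall is 1 − 1.5/c. The values of c are illustrations.
- c = 1.6: 1 − 1.5/1.6 = 1 − 0.9375 = 6.25%, about 6%.
- c = 2.0: 1 − 1.5/2.0 = 25%.

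A patient who rises from 1.6 to 1.7 and returns to 1.6 has recovered fully but still fails the resume test.

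**3. The 6-week clock.** Six weeks is 42 days. Take the month of taper as 28 days, its shortest reading.
- Time left for creatinine to reach Grade 1 or lower before the taper must start, if avelumab is the next drug due: 42 − 28 = 14 days.
- If rhIL-15 is the next drug due, with the steroid-free week: 42 − 28 − 7 = 7 days.

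This clock is the same for every patient in the row. What is particular to the clearance route is that a patient whose creatinine settles at the entry value never meets the condition, so the 6-week limit ends treatment.

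**4. Effect on the MTD count.** Avelumab is first given on Day 8 (Section 3.1), so an avelumab-related renal event in cycle 1 would come after that dose. The chemistry check before the Day 22 dose is the next scheduled check that Section 3.6 shows. A hold there interrupts cycle 1. If the event is not a DLT, Section 10.2 may make the patient unevaluable. I say may, because the section does not state whether a patient on hold at Day 28 has finished the cycle. The patient stays in the toxicity population under Section 10.3.1.

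**5. Room for replacements.** The evaluable totals in Section 10.2 reproduce: 3 × 6 + 9 = 27 at most and 3 × 3 + 9 = 18 at least. Against the ceiling of 30, spare places run from 30 − 27 = 3 to 30 − 18 = 12. Each replaced patient uses one.

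**The case against.** The strongest reply is that Table 10 covers immune-related adverse events and is worded as an increase. Section 8.1.1 ties an adverse event to administration of a product. Section 6.1.1 records events from the first study intervention. Section 6.1.2.1 makes an abnormal laboratory value an adverse event only under listed conditions. An unchanged pre-treatment creatinine therefore does not qualify. This stands, and it disposes of a stronger reading that a reader might infer: that such patients are held or removed on Day 1, or at the Day 8 check, simply for having their baseline value. Before Day 8 no avelumab has been given, so a stable value cannot be an avelumab reaction.

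The reply does not cover a later rise. Once a rise is judged immune-related, Table 10 applies in full, and nothing in it adjusts the resume point for where the patient began. The protocol refers to baseline when it wants to: Section 3.1.1.2 does so for liver tests in patients with baseline elevations, and Table 6 does so for stool frequency.

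A reader might also infer a second conflict, on steroids. Section 2.1.2.6 allows "Systemic corticosteroids at physiologic doses ≤ 10 mg/day of prednisone or equivalent", while Table 13 ends protocol therapy for "Requirement for 10 mg per day or greater prednisone or equivalent for more than 12 weeks". The documents do not support this as a stop at entry. The Table 13 row needs more than 12 weeks, excludes adrenal replacement and sits in a table of immune-related events. Counted from Day 1, it could not apply before Day 85 (12 × 7 = 84 days completed). The two ranges share only the single value of 10 mg/day.

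**Conclusion.** The point holds for creatinine in a limited form. For a patient enrolled above 1.5 x ULN, a small rise judged immune-related triggers the hold-and-steroid row, and the condition for restarting lies below the patient's entry value. With the joint hold and the 6-week limit, a patient who recovers only to baseline is removed.

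This rests on two conditions: the rise qualifies as an adverse event, and the investigator judges it immune-related. The effect on the MTD count needs two more: the hold falls in cycle 1, and the event is not a DLT.

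The documents do not give the number of patients who would enter through the clearance route, and it is probably small. The escalation probabilities and the sample-size arithmetic are untouched. The point still deserves correction, because a stated rule is unworkable for patients whom the protocol expressly admits, and following it exposes them to systemic steroids. The steroid limits are at most a matter for clarification at 10 mg/day.

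**What to change.** Reconcile Section 2.1.1.7, Section 3.3 and Table 10 so that the hold and resume conditions can be applied to a patient enrolled with creatinine above 1.5 x ULN. Table 10 should say how its thresholds are to be read for such a patient. Which limit governs is for the sponsor's clinicians, and no threshold is proposed here.

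In Section 10.2, add a sentence on whether a patient whose first cycle is interrupted by such a hold, without a DLT, counts as having finished the cycle.

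Optionally, state whether a 10 mg/day prednisone dose permitted at entry under Section 2.1.2.6 counts toward the 12-week row of Table 13.

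The cost is a few lines of protocol wording in an amendment, with no added patients, visits or procedures.
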